#### **8.1.2 Clinical Pharmacology**

DSF is mostly known as an irreversible inhibitor of aldehyde dehydrogenase, which affects alcohol metabolism and causes accumulation of acetaldehyde. However, increasing preclinical studies have shown that DSF is also a proteasome inhibitor, specifically the chymotrypsin-like activity. GBM cells and its stem-like subpopulation (also referred to as CSC) may be more susceptible to the effect of

proteasomal inhibition than normal brain cells. DSF is very lipophilic and readily crosses the blood-brain barrier.

### **8.1.3 Supplier**

DSF (trade name Antabuse) is commercially available and will be provided to participants by the study.

### **8.1.4 Dosage Form**

DSF is supplied as white, round tablets of 250 mg. Each tablet also contains colloidal silicon dioxide, anhydrous lactose, magnesium stearate, microcrystalline cellulose, sodium starch glycolate, and stearic acid. The tablet may be cut in half to obtain 125 mg dose.

### **8.1.5 Storage and Stability**

DSF is dispensed in a tight, light-resistant container. It should be stored at controlled room temperature (20° to 25°C or 68° to 77°F) in its original container to protect from bright light.

### **8.1.6 DSF Administration**

[figure not shown]
DSF is taken by mouth daily. It should be taken with meal to improve absorption. It should not be taken within one hour of temozolomide. Patient should not have consumed any alcohol at least 12 hours prior to the first dose. In the rare event of a severe hypersensitivity reaction, discontinue DSF immediately.

## **8.2 Temozolomide (Temodar)**

### **8.2.1 Temozolomide Description**

Chemical name: 3,4-dihydro-3-methyl-4-oxoimidazo[5,1-d]-*as*-tetrazine-8-carboxamide.

Structural formula:

### **8.2.2 Clinical Pharmacology**

Temozolomide is not directly active but undergoes rapid nonenzymatic conversion at physiologic pH to the reactive compound 5-(3-methyltriazen-1-yl)-imidazole-4-carboxamide (MTIC). The cytotoxicity of MTIC is thought to be primarily due to alkylation of DNA. Alkylation (methylation) occurs mainly at the O and N positions of guanine.

### **8.2.3 Pharmacokinetics and Drug Metabolism**

Temozolomide is rapidly and completely absorbed after oral administration with a peak plasma concentration ( $C_{max}$ ) achieved in a median  $T_{max}$  of 1 hour. Food reduces the rate and extent of temozolomide absorption.

Temozolomide is spontaneously hydrolyzed at physiologic pH to the active species, MTIC and to temozolomide acid metabolite. MTIC is further hydrolyzed to 5-amino-imidazole-4-carboxamide (AIC), which is known to be an intermediate in purine and nucleic acid biosynthesis, and to methylhydrazine, which is believed to be the active alkylating species. Cytochrome P540 enzymes play only a minor role in the metabolism of temozolomide and MTIC.

About 38% of the administered temozolomide total radioactive dose is recovered over 7 days: 37.7% in urine and 0.8% in feces. Temozolomide is rapidly eliminated, with a mean elimination half-life of 1.8 hours.

### **8.2.4 Supplier**

Temozolomide is commercially available.

### **8.2.5 Dosage Form and Preparation**

Temozolomide capsules are supplied in child-resistant sachets containing the following capsule strengths: 5 mg, 20 mg, 100 mg, 140 mg, 180 mg, and 250 mg.

### **8.2.6 Storage and Stability**

Store temozolomide capsules at 35°C (77°F); excursions permitted to 15-30°C (59-86°F).

### **8.2.7 Administration**

Please refer to Sections 5.6 and 5.9.

### **8.2.8 Special Handling Instructions**

The use of gloves is recommended.

## **9.0 CORRELATIVE STUDIES**

The correlative studies to measure drug concentration will be performed in all enrolled patients that have agreed to take part in collection of blood and tumor samples. Drug concentration of DSF metabolites (such as ditiocarb-copper complex) from the serum and tumor samples will be measured by mass spectrometry by our collaborator [name] at Palacky University

Olomouc in Czech Republic as previously described [71]. **Of note, the tumor, plasma, cell pellet or lysate may be stored at -80 °C for up to 2 years before batch analysis.**

### **9.1 Collection of Specimens**

If a patient is participating in the optional tumor collection at time of recurrence, a tumor specimen of at least 0.2 cubic cm or approximately 200 mg will be collected. At the time of salvage surgery, approximately 20 mL of peripheral blood (10 mL into each of 2 green top tube containing sodium heparin) will also be collected. Tumor and blood samples will be submitted at ambient temperature to Tissue Procurement Core (TPC) for processing and storage.

## 10.0 STUDY CALENDAR

### 10.1 Dose-escalation phase:

Baseline evaluations are to be conducted up to 14 days prior to start of pre-operative DSF. Labs and MRIs must be done no more than 30 days prior to the start of the protocol therapy.

	B/I	3 days pre-surg 	Surg 	Pre-RT 	Wks 1-6 	Adjuvant TMZ  Cycles						F/U 
						1	2	3	4	5	6	
Informed consent	X											
Physical exam	X			X	X 	X	X	X	X	X	X	
KPS	X			X								
CBC	X		X	X	X 	X	X	X	X	X	X	
BMP	X		X	X	X 	X	X	X	X	X	X	
LFTs	X		X	X	X 	X	X	X	X	X	X	
β-hCG 	X			X								
MRI w/ and w/o contrast	X			X 			X		X		X	
Path. conf. of GBM diagnosis				X								
RT					X 							
Temozolomide					X 	X 	X 	X 	X 	X 	X 	
DSF		X 			X 	X 	X 	X 	X 	X 	X 	
Cu 		X 			X	X	X	X	X	X	X	
Review of medication diary			X		X 							
Adverse events		X		X	X 	X 	X 	X 	X 	X 	X 	X 
Collection of tumor 			X									
Collection of blood			X									

1. Weekly during RT + TMZ
2. Women of childbearing potential only
3. Daily during RT
4. Days 1-5 of every 28-day cycle
5. Adjuvant TMZ will start 4-6 weeks after the end of RT and will be given for 6 28-day cycles
6. 500 mg daily with adjuvant TMZ
7. 2 mg TID with meals while taking DSF
8. Reviewed weekly by the treating radiation oncologist or the institutional PI during concurrent RT + TMZ, and reviewed every 8 weeks during adjuvant TMZ.
9. Only if patient is still receiving DSF
10. DSF/Cu are taken for 3 days prior to surgery, and preoperative DSF should be taken in the evening approximately 1 hour before or 1 hour after dinner. The dose of DSF is as per dose-escalation criteria.
11. DSF is taken in the morning approximately 1 hour before or 1 hour after breakfast. The dose of DSF is as per dose-escalation criteria
12. Must be resection with at least 200 mg of tissue available beyond what is required for pathology. This is only required for patients that have opted into the preoperative DSF + Cu phase of treatment.
13. For patients consented for the optional preoperative DSF, eligibility must be reconfirmed after surgery and before the start of RT. For patients consented after surgery, they need to meet eligibility prior to RT.
14. RT and TMZ will start 4-6 weeks after resection (up to 8 weeks is permissible)
15. 30 fractions of RT given over 6 weeks
16. The patient will be followed for 30 days after the last dose of disulfiram for adverse events; 2 years after coming off study, a review of the patient's medical records will be conducted to collect data on progression and survival
17. If the tumor recurs during the 6-month treatment period and the patient has surgery, we will request a portion of the tissue removed during surgery for future correlative studies

18. OPTIONAL; patients whose disease recurs and who will undergo another resection may opt to take p 5 days (+/- 2 days) of preoperative DSF (250 mg per day in the morning) and Cu (2mg PO TID with meals) until the day before the planned surgery. Patient should not take DSF/Cu on the day of surgery.

19. Simulation MRI can be used as pre-RT MRI if conducted with and without contrast

20. Monthly during RT + TMZ.

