### 1.2.8 Measurement of Intratumoral Drug Concentration using Resected Tumors

Although no studies have analyzed uptake of DSF and its metabolites in gliomas, a few prospective studies have investigated intracranial drug penetration by administering chemotherapy before planned resection of brain tumors. In a study measuring cisplatin level, high-grade gliomas appeared to have higher drug

concentration than low-grade gliomas but lower when compared to brain metastases, suggesting break-down of the blood-brain barrier plays an important factor in intratumoral drug concentration [54]. Previous studies have shown a sample size of 5 is typically sufficient to detect difference in drug concentration between dose levels [55]. Given the tumor specimen invariably contain blood, high plasma concentration may lead to over-estimation of the tissue drug concentration [56]. Thus, an accurate estimation of intratumoral drug concentration would require measurement of concurrent plasma level and would ideally be measured when the plasma level has peaked.

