## **5.7 Optional Preoperative Disulfiram before Salvage Surgery**

After completion of adjuvant DSF, patients should be followed every 2-3 months as per routine clinical care. If a patient develops recurrent tumor during follow-up and plans to undergo another resection, he/she may opt for an optional preoperative DSF study prior to salvage surgery. Patients who would like to participate in this optional portion of the study will be treated with a 5-day (+/- 2 days) lead-in with oral DSF and Cu. DSF should be taken as 250 mg per day approximately 1 hour after dinner in the evening, and Cu should be taken as 2mg TID with each meals. Patient should not take DSF or Cu on the day of the surgery and should complete the drug diary (Appendix E).

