15. Reviewed weekly by the treating radiation oncologist or the institutional PI during concurrent RT + TMZ, and reviewed every 8 weeks during adjuvant TMZ.
16. If patient is still receiving DSF/Cu on study, they should continue until the day before the planned surgery. If they are off DSF/Cu at time of recurrence, they may opt to take 5 days (+/- 2 days) of preoperative DSF (250 mg per day in the evening) and Cu (2mg PO TID with meals) until the day before the planned surgery. Patient should not take DSF/Cu on the day of surgery.
17. A portion of resected tumor tissue and blood will be collected for future correlative studies.

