### INSTRUCTIONS TO THE PATIENT:

1. Complete this form for the pre-surgery doses of disulfiram (3-7 doses). Take 250mg (1 tablet) of disulfiram daily at approximately the same time each day (you should take with 8 ounces of water approximately **1 hour after DINNER in the EVENING**). Please also take 2 mg of copper gluconate supplement three times a day with each meal. **You should not take disulfiram nor copper on the day of surgery.**
2. Record the date, what time you took disulfiram on that date, and how many times you took copper supplement on that date.
3. If you have any questions or notice any side effects, please record them in the comments section. Record the time if you should vomit.
4. Please return the forms to your physician or your study coordinator on the day of surgery.
5. Avoid consuming alcohol before and throughout the entire study.

Day	Date	What time was Disulfiram taken?	How many times was the copper supplement taken	Comments
1				
2				
3				
4				
5				
6				
7				

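### The optional disulfiram lead-in before salvage surgery is a morning dose in one study calendar and an evening dose in three other places, which shifts the dose-to-sample interval of a secondary concentration endpoint

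*Combined protocol and SAP*

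**What the plan says.** Four places give a time of day for the DSF lead-in offered when a patient recurs and is to have another resection:

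- Calendar 10.1 (dose escalation), note 18: "preoperative DSF (250 mg per day in the morning".
- Section 5.7: "DSF should be taken as 250 mg per day approximately 1 hour after dinner in the evening".
- Calendar 10.2 (dose expansion), note 16: "preoperative DSF (250 mg per day in the evening".
- Appendix E, the patient's diary for these doses: "1 hour after DINNER in the EVENING".

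The four agree on 250 mg per day and on omitting the drug on the day of the operation (calendar 10.1: "Patient should not take DSF/Cu on the day of surgery"). They also agree on length: five days plus or minus two, or three to seven doses in the diary. Section 5.7 and Appendix E are not limited to one phase of the study. A separate note 10 in calendar 10.1, for the three-day lead-in before the initial surgery, reads "preoperative DSF should be taken in the evening approximately 1 hour before or 1 hour after dinner".

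Section 9.1 provides for tumour and blood at salvage surgery. Concentration of the ditiocarb-copper complex in plasma and tumour is a secondary endpoint (Sections 2.0 and 14.2). Section 14.4 plans the median and range, and Cox models relating intratumour concentration to tumour control and survival. Section 1.2.8 says that an accurate intratumour estimate needs a concurrent plasma level and "would ideally be measured when the plasma level has peaked".

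**The concern.** An escalation patient who recurs and takes the lead-in has a calendar that says morning and a diary that says evening. The end of dose finding does not close the conflict, because recurrence can come much later.

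What is at stake is comparability of the concentration samples. Since the last dose falls on the day before surgery in every version, a morning dose leaves a longer gap to sampling than an evening dose. If both timings occur and the gap is not reported, part of the spread in the concentration summary reflects when the tablet was taken. The same difference would enter the concentration-outcome models. Section 14.4 does not mention the interval from last dose to sampling. With few optional samples, one or two taken at a different interval could set the range or move the median.

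**Working it through.** The plan states no sample size, power or effect figure for this endpoint, so there is no figure of its own to reproduce.

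**Inputs from the protocol.** Section 1.2.7 gives half-lives of 7.3 h (DSF), 15.5 h (DDTC) and 22.1 h (Me-DDTC), and an average time to peak of 8 to 10 h for DSF and its metabolites. Section 5.7 places the evening dose about 1 h after dinner. No half-life is given for the ditiocarb-copper complex.

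**Assumptions.** The documents give no clock time for meals, doses or surgery. I take the morning-to-evening shift as 9 to 12 h.

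**Step 1, decay only.** The ratio of concentration after an evening dose to that after a morning dose is 2^(shift / half-life).

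| Shift | DSF | DDTC | Me-DDTC |
|---|---|---|---|
| 9 h | 2.35 | 1.50 | 1.33 |
| 10 h | 2.58 | 1.56 | 1.37 |
| 11 h | 2.84 | 1.64 | 1.41 |
| 12 h | 3.12 | 1.71 | 1.46 |

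For example, DDTC at 12 h gives 2^(12/15.5) = 1.71. This step treats absorption as complete well before either sample, which does not fit a peak at 8 to 10 h.

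**Step 2, allowing for the stated time to peak.** I used a one-compartment model with first-order absorption and n daily doses added together:

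C(t) = Σ ka/(ka − ke) × [exp(−ke(t + 24i)) − exp(−ka(t + 24i))], for i = 0 to n − 1,

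with ke = ln 2 / half-life and ka solved from ln(ka/ke)/(ka − ke) = time to peak. Times to peak were 8, 9 and 10 h, and n was 3, 5 and 7. The assumed sampling times after the last dose (evening versus morning) were 12 v 24, 13 v 23, 15 v 25, 18 v 28 and 17 v 29 h.

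Worked case, DDTC with peak at 8 h and five doses: ke = 0.0447 and ka = 0.269 per hour; C(12) = 1.013 and C(24) = 0.618 in relative units; the ratio is 1.64.

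Over all cases, evening/morning:

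- DSF: 1.64 to 2.53
- DDTC: 1.43 to 1.69
- Me-DDTC: 1.32 to 1.45

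The number of doses makes almost no difference. A 9 h shift (12 v 21, 13 v 22, 15 v 24 and 18 v 27 h, five doses) gives 1.36 to 1.48 for DDTC and 1.27 to 2.00 over the three species, so the rounded lower ends below still hold.

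**Step 3, reading across to the endpoint.** Treating DDTC as a proxy for its copper complex is an assumption. On that basis the shift is worth about 1.4- to 1.7-fold. The three listed species together span about 1.3- to 2.5-fold. For scale, the two dose levels used in escalation (Section 1.3) differ by 375/250 = 1.5-fold. If exposure were proportional to dose (a further assumption), the timing effect would be about the size of that step.

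**Step 4, patients still taking DSF at recurrence.** Note 16 of calendar 10.2 has them continue until the day before surgery. Section 5.6 refers to Section 5.7 for the timing of adjuvant DSF, which is the evening. The Appendix G diary for the same doses says one hour after breakfast. The adjuvant dosing notes in the calendars (note 6 of 10.1 and note 13 of 10.2) give no time of day. Reconciling note 18 alone would therefore not give all salvage samples one interval.

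**The case against.** The reach is narrow. Note 18 belongs to the calendar of a phase whose 18 patients are already enrolled. It matters only for those who recur, have another resection and choose the lead-in, and the documents do not say how many that is. The sheet such a patient fills in, Appendix E, prints one time of day. Note 18 is also attached to the pre-surgery column of calendar 10.1, where the DSF cell itself carries note 10. All of this stands, and it limits the severity. It does not remove the contradiction, because site staff work from the calendar and patients from the diary.

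Section 1.2.8 makes the concurrent plasma level the required element and peak timing only the ideal, and blood at salvage surgery is already planned in Section 9.1. That is correct. A reader might infer that the protocol demands sampling at peak; it does not.

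Section 14.4 does not say that samples with different dosing times will be pooled. That is also true, but it neither separates them nor asks for the interval to be shown.

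A reader might infer from the half-lives that the secondary endpoint changes 1.5- to 3-fold. The documents do not support that. The 3-fold end (3.12) is parent DSF under pure decay with a full 12-hour shift, and parent DSF is not the endpoint analyte. Once the stated time to peak is allowed for, 3-fold is not reached in any case tried. The half-lives come from plasma studies in alcoholic patients, and Section 1.2.7 says that levels in glioma have not been measured, so no factor for tumour tissue can be derived.

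**Conclusion.** The contradiction holds: one timing in note 18 of calendar 10.1, the other in Section 5.7, note 16 of calendar 10.2 and Appendix E, for the same lead-in at the same dose. It moves dose-to-sample time by roughly 9 to 12 hours, on assumed meal and surgery times.

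The size for the endpoint analyte is not derivable. About 1.4- to 1.7-fold is an estimate that rests on DDTC standing in for the ditiocarb-copper complex and on a simple absorption model fitted to the stated time to peak. The range of about 1.3- to 2.5-fold covers the three listed species under the same model. Section 5.6 and Appendix G add a parallel conflict for patients still on adjuvant DSF at surgery.

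Severity is minor. The samples are optional, the analysis is descriptive with exploratory models, few escalation patients are likely to be affected, and neither the primary endpoint nor any decision rule depends on it. This review takes no position on which time of day is right.

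**What to change.** 1. Reconcile note 18 of calendar 10.1, Section 5.7, note 16 of calendar 10.2 and Appendix E so that one timing is stated. Do the same for Section 5.6 and Appendix G. The choice of timing is for the investigators.
2. In Section 9.1, require the clock time of tumour and blood collection to be recorded. The diaries capture dose times, but no section requires a collection time, so the interval cannot be counted on from what is planned now.
3. In Section 14.4, report each concentration alongside its interval from last dose to sampling. If the number of samples allows, repeat the concentration-outcome model with adjustment for that interval as a sensitivity analysis. With few samples the adjusted model may not be estimable, so it should not be the main analysis.

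The cost is wording changes in a few places, one extra recorded time per specimen and a small amount of analysis. Sample size and the primary analysis are unaffected.

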### **10.2 Dose-expansion phase:**

Baseline evaluations, labs and MRIs must be done no more than 30 days prior to the start of the protocol therapy.

	B/I	Wks 1-6 	Adjuvant TMZ  Cycles						F/U 	Optional: Tissue collection at recurrence 
			1	2	3	4	5	6		
Informed consent	X									X
Physical exam	X	X 	X	X	X	X	X	X		
KPS	X									
CBC	X	X 	X	X	X	X	X	X		
BMP	X	X 	X	X	X	X	X	X		
LFTs	X	X 	X	X	X	X	X	X		
β-hCG 	X									
MRI w/ and w/o contrast	X 			X		X		X		
Path. diagnosis of GBM with IDH, BRAF, or NF1 mutations	X									
RT		X 								
Temozolomide		X 	X 	X 	X 	X 	X 	X 		
DSF		X 	X 	X 	X 	X 	X 	X 		X 
Cu 		X	X	X	X	X	X	X		X 
Review of medication diary		X 								X
Adverse events		X 	X 	X 	X 	X 	X 	X 	X	X
Collection of tumor										X 
Collection of blood										X 

1. RT and TMZ will start 4-6 weeks after resection (up to 8 weeks is permissible)
2. Adjuvant TMZ will start 4-6 weeks after the end of RT and will be given for 6 28-day cycles
3. The patient will be followed for 30 days after the last dose of disulfiram for adverse events; 2 years after coming off study, a review of the patient's medical records will be conducted to collect data on progression and survival
4. If a patient develops recurrence and is eligible for salvage surgery, he/she will be eligible for optional tissue collection at time of salvage surgery. If he/she is not on DSF/Cu any more, he/she may opt to take 5 days (+/- 2 days) of preoperative DSF and Cu before the planned surgery.
5. Weekly during RT + TMZ
6. Monthly during RT + TMZ.
7. Women of childbearing potential only
8. Simulation MRI can be used as pre-RT MRI if conducted with and without contrast
9. 60 Gy in 30 fractions
10. 75 mg/m^2 daily during RT
11. Days 1-5 of every 28-day cycle
12. DSF is taken in the morning approximately 1 hour after breakfast. The dose of DSF in the expansion cohort is 250 mg once daily during RT.
13. DSF dose during adjuvant TMZ will be 500 mg once daily
14. 2 mg TID with meals while taking DSF

15. Reviewed weekly by the treating radiation oncologist or the institutional PI during concurrent RT + TMZ, and reviewed every 8 weeks during adjuvant TMZ.
16. If patient is still receiving DSF/Cu on study, they should continue until the day before the planned surgery. If they are off DSF/Cu at time of recurrence, they may opt to take 5 days (+/- 2 days) of preoperative DSF (250 mg per day in the evening) and Cu (2mg PO TID with meals) until the day before the planned surgery. Patient should not take DSF/Cu on the day of surgery.
17. A portion of resected tumor tissue and blood will be collected for future correlative studies.

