Given its long track record of safety when used alone, especially below 1000 mg, DSF should pose minimal risk when given to presumed GBM patients before their surgical resection. Although patients without histological confirmation would qualify for this study, a misdiagnosis of GBM based on MRI finding is relatively uncommon. Furthermore, since it is not a cytotoxic chemotherapy, a short-course administration of pre-operative DSF for 3 days to a patient with a different diagnosis should not adversely affect his/her subsequent treatment. As for overlapping toxicity with TMZ or RT, DSF appears to have preferential inhibition of tumor MGMT versus liver MGMT *in vitro*, and our previous phase I study demonstrated safety when combining it with TMZ. Since DSF may be radiosensitizing due to its possible effect on DNA repair based on *in vitro* studies, its tolerability with RT is currently unknown. To monitor for severe toxicity, patients will be followed frequently during RT with weekly clinical evaluation and CBC. Liver function test will be checked before starting DSF, and every month while taking DSF.

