## 6.2 DSF Dose Modifications

During radiotherapy, if a patient experiences any adverse event that requires dose reduction in the opinion of the investigator and that is considered by the investigator to be possibly, probably, or definitely related to DSF, DSF/Cu should be discontinued and the event will be considered a DLT. If RT has to be temporarily interrupted for technical or medical reasons unrelated to TMZ or DSF/Cu, then treatment with daily TMZ and DSF/Cu should continue. If RT has to be permanently discontinued then TMZ and DSF/Cu should stop until re-initiated at the adjuvant phase of treatment. If TMZ is held due to toxicity unrelated to DSF/Cu, DSF/Cu should continue as tolerated.

During adjuvant TMZ, the dose of DSF may be reduced from 500 mg per day to 250 mg per day due to toxicity or intolerance at the discretion of the treating physician. Expansion patients who discontinued DSF during RT and concurrent TMZ due to toxicity may be considered to resume DSF with adjuvant TMZ but at 250 mg/day as long as the toxicity has resolved prior to the start of cycle 1 of adjuvant TMZ and after discussion between the treating physician and the PI. Special attention should be paid to neurological symptoms such as delirium/psychosis, gait disturbance/ataxia, and peripheral neuropathy. A grade 2 toxicity of the above neurological symptoms should prompt a consideration for further work-up and consideration of dose reduction if thought to be related to DSF. No second dose reduction (below 250 mg/day) is allowed—if a second dose reduction is required, DSF and Cu will be permanently discontinued. Of note, hematologic toxicity is uncommon for DSF and is likely related to TMZ.

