### **6.2.1 Administration of DSF to Patients with Abnormal Hepatic Function**

DSF/Cu should only be administered if hepatic function is within the parameters established in the eligibility criteria. Hepatic toxicity from DSF/Cu is uncommon but may occur. Therefore, hepatic dysfunction that occurs while the patient is on study should prompt an evaluation to determine the cause, including the possibility of hepatotoxicity from concurrent medications including TMZ.

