### **6.2.2 Hypersensitivity Reactions**

Hypersensitivity reactions rarely occur. If they do occur, minor symptoms such as flushing, skin reactions, dyspnea, lower back pain, hypotension, or tachycardia may require no intervention; however, severe reactions, such as hypotension requiring treatment, dyspnea requiring bronchodilators, angioedema, or generalized urticaria require immediate discontinuation of study drug administration and aggressive symptomatic therapy. Patients who experience a severe hypersensitivity reaction to DSF should discontinue DSF immediately and should not be re-challenged.

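### The expansion-phase calendar lets any patient who is off DSF/Cu restart it before salvage surgery, which conflicts with the permanent-stop and no-re-challenge rules of Section 6, and it schedules no liver test for that restart.

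*Combined protocol and SAP*

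**What the plan says.** **Permission.** Section 10.2 (dose-expansion calendar), note 4: "If he/she is not on DSF/Cu any more, he/she may opt to take 5 days (+/- 2 days) of preoperative DSF and Cu" before the planned operation. Note 16: "If they are off DSF/Cu at time of recurrence, they may opt to take 5 days (+/- 2 days) of preoperative DSF", at 250 mg per day in the evening with copper three times daily. Appendix E gives the same dose and counts 3 to 7 doses. Section 5.7 describes the same option but opens with: "After completion of adjuvant DSF, patients should be followed every 2-3 months as per routine clinical care". It then offers the course to a patient who recurs during follow-up and plans another resection.

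**Restrictions.** Section 6.2, on dose reduction in the adjuvant phase, allows no step below 250 mg/day: "if a second dose reduction is required, DSF and Cu will be permanently discontinued". Section 6.2.2, on severe hypersensitivity, says such patients "should discontinue DSF immediately and should not be re-challenged". Section 6.2.1 states: "DSF/Cu should only be administered if hepatic function is within the parameters established in the eligibility criteria". Section 1.2.10 adds: "Liver function test will be checked before starting DSF, and every month while taking DSF".

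**Calendar cells.** The column headed "Optional: Tissue collection at recurrence" marks consent, DSF, Cu, diary review, adverse events, tumour and blood. Its LFT cell is empty.

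**The concern.** Notes 4 and 16 never ask why DSF/Cu was stopped. A patient who finished six adjuvant cycles and a patient taken off the drug for good both count as off DSF/Cu. Someone working from the calendar would offer both of them the course. Someone working from Section 6 would refuse the second.

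The dose makes the conflict concrete. Section 6.2 stops the drug permanently when a patient needs to go below 250 mg/day, and the pre-surgery course is given at 250 mg/day.

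What is at stake is participant safety, not the survival analysis. The course supports correlative work on tumour and blood, and the calendar text could invite re-exposure that another section of the same protocol rules out. The empty LFT cell is a smaller, related problem: the person applying Section 6.2.1 has no scheduled result to apply it to. Raised liver enzymes accounted for two of the three dose-limiting toxicities in the escalation phase (Section 1.3).

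**Working it through.** The plan states no figure for this point, so the check is a reading of the passages against each other.

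**Step 1. Who meets the calendar's condition, and what does Section 6 say about them?**

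| Patient at recurrence | Notes 4 and 16 | Section 6 |
|---|---|---|
| Completed adjuvant DSF without stopping | May take the course | No bar, subject to 6.2.1 |
| Stopped during RT for toxicity | May take the course | 6.2 allows a resumption at 250 mg/day in the adjuvant phase if the toxicity has resolved before cycle 1 and the treating physician and PI have discussed it |
| Needed a second reduction in the adjuvant phase | May take the course | 6.2: permanent stop |
| Severe hypersensitivity to DSF | May take the course | 6.2.2: no re-challenge |

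The last two rows are direct conflicts. In the second row, Section 6.2 attaches conditions to the one resumption it allows, and notes 4 and 16 carry no counterpart.

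**Step 2. Does Section 5.7 settle it?** Its opening can be read as confining the option to patients who completed adjuvant DSF. On that reading it is narrower than notes 4 and 16, which cover anyone off drug. It can also be read as only setting the follow-up interval; then it contains no exclusion and the conflict in Step 1 stands. Reconciliation is needed on either reading.

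**Step 3. Are liver tests scheduled for the restart?** In the LFT row of Section 10.2, baseline, weeks 1 to 6 and cycles 1 to 6 are marked, while the follow-up and optional columns are blank. For a patient who recurs after the adjuvant cycles, the last scheduled result is therefore from cycle 6 or earlier. For a patient still in the cycles, a result exists but is not tied to the restart. By contrast, the escalation calendar (Section 10.1) asks for baseline evaluations within 14 days before its preoperative DSF and marks LFTs at surgery. Section 10.2 has no equivalent line for its own pre-surgery course.

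**Step 4. Can the number affected be derived?** The two available rates are:
- escalation-phase DLTs (Section 1.3): 3/18 = 16.7%;
- stops for possibly DSF-related toxicity at 500 mg in the earlier phase I study (Section 1.2.6): 2/7 = 28.6%.

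Applied to the 15 further patients, these give 15 × 0.167 = 2.5 and 15 × 0.286 = 4.3. That range counts toxicity of any kind, which is not the group Section 6 bars:
- None of the five events is described as a second dose reduction or a hypersensitivity reaction.
- Both patients in the 2/7 had toxicity that resolved after stopping.
- The 3/18 pools two doses: 1/8 = 12.5% at 250 mg/day, the expansion dose during RT, and 2/10 = 20% at 375 mg/day, where both hepatic events occurred.

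Recurrence, a planned resection and opting in must also occur, and the documents give no rate for any of these. The number wrongly re-exposed is not derivable.

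**The case against.** The strongest reply is that Section 6 already governs. Sections 6.2.1 and 6.2.2 are unqualified, notes 4 and 16 only say that a patient may choose the course, and nothing in the calendar claims to override Section 6. The option also has its own consent step, diary review and adverse-event review.

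For 6.2.1 and 1.2.10 this stands. A reader might infer that the calendar contradicts them, but an empty cell does not cancel a rule; it leaves the rule without its scheduled input. For 6.2 and 6.2.2 the reply does not suffice. A permission whose only condition is being off drug, set against a permanent stop and a bar on re-challenge, is a conflict on the face of the text, and no order of precedence is stated.

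It is also fair that most toxicity stops are not barred. Section 6.2 itself permits a conditional resumption at 250 mg/day, so only the second-reduction and severe-hypersensitivity patients are expressly excluded.

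A reader might further infer that a pregnancy test and the 7-day interacting-drug rule are already required before this restart. The documents do not say so: Sections 3.2 and 5.11 tie them to the start of treatment or the first dose. Nor do they show that contraception has lapsed, because Section 5.11 covers participation in the study as well as the 4 months after the last dose. Whether these rules extend to the restart is simply unstated.

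**Conclusion.** The concern holds in two parts of unequal weight. First, notes 4 and 16 of Section 10.2 conflict with Sections 6.2 and 6.2.2 for two identifiable groups, and they are broader than Section 5.7 if its opening phrase limits the option. Second, the same calendar leaves out the liver result needed to apply Section 6.2.1.

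The size per patient is 3 to 7 daily doses at 250 mg. The count of patients is unknown. A reader might infer that 3 or 4 of the 15 new patients would be re-exposed against the protocol, but that figure counts all toxicity stops and does not measure the barred group, which is smaller.

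The conclusion rests on reading notes 4 and 16 as they are worded. The consent text was not available, so any further conditions there could not be checked. The point does not touch the overall survival endpoint or the sample size. It still deserves correction before the option is used, because a single patient restarted against Section 6.2 or 6.2.2 would have been restarted on the strength of the protocol's own calendar.

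**What to change.** 1. Reconcile notes 4 and 16 of Section 10.2 and Section 5.7 with Sections 6.2, 6.2.1 and 6.2.2, so that one stated set of conditions governs re-exposure before salvage surgery. Either repeat it in each place or put it in one place and cross-refer.
2. Bring the LFT row of the optional recurrence column in Section 10.2 into line with Sections 6.2.1 and 1.2.10.
3. State whether the pregnancy-test and interacting-drug rules of Sections 3.2 and 5.11, now tied to treatment start or first dose, apply to this restart.

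Which conditions should apply is for the sponsor and investigator to decide; no clinical rule is proposed here.

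The cost is protocol wording and a routine blood test. The downside is possibly a few fewer on-drug tumour samples. Tissue collection itself is not lost, because note 4 already makes patients eligible for it without the pre-surgery course.
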